Judgment criteria	
The main judgment criterion for the HR will be the evaluation of the concordance between the measurements obtained following the application of the reference technical processes of non-operator dependent measurement taking via a CE marked device and via COBOX.
 
The secondary judgment criterion associated with the measurement of the RR will also be the subject of an evaluation of the concordance between the measurements obtained via a reference method of manual counting

	
according to the good practices of the medical or paramedical nursing staff (or arc or tec) and via COBOX.
 
For each of the parameters measured, we will establish the repeatability of the measurement and its accuracy (comparison of the relative error expressed as a percentage between the two types of measurement).

Study size	323 patients
Planned number of centers	4
Search duration	
Duration of participation for each patient: less than 30 minutes
 
Total research duration: 3 months
 
Approximate study start date: mid-July 2022
 
Approximate study end date: mid-October 2022

Statistical analysis of data	
The performance of the tool will be estimated by the concordance between the measurements obtained from the application of the reference technical process via a CE marked device and with the measurements obtained by COBOX.
 
An intraclass correlation coefficient (ICC) with its 95% confidence interval (95% CI) will be calculated. Measurement errors will be calculated and expressed as a percentage (root mean square error, etc.).
 
The two study samples will be compared by Student's t test and Fischer's F, with a desired significance for P value = 0.05, for all the analyses.
 
A DIXON test will be performed to assess the presence of statistically outliers within the samples.

Expected benefits	
These data will enable the COBOX tool, a class IIA medical device, to be validated in terms of measurement performance compared to a CE-marked device used in a reference technical process for taking measurements and a reference method for manual counting. Applications for taking constants without contact have a wide field of application in

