The name of the SaaS API is COBOX, a software-only solution.

As part of this study, we will use “COBOX” version 1.0.0.

During the clinical investigation, this API will be integrated into the “DemoCOBOX” version 0001 application in order to allow its use by medical personnel (or arc or tec) . This application will be installed on a Samsung S6 tablet. The tablet will be placed on a tablet support equipped with an anti-theft device.

Description of how traceability should be ensured during and after the clinical investigation, for example by assigning batch, batch or serial numbers.

During the clinical investigation, Quantiq.io will keep an identical model of the tablet with the same version of COBOX installed in order to be able to reproduce any possible deviation in a measurement and to investigate whether it comes from the tablet or the clinical trial conditions. The reference of each tablet distributed for the trial as well as the DemoCOBOX application version installed on it will be stored on our servers. The use of the application may be monitored on our servers. Quantiq reserves the right to make extremely minor patches to the API as well as the demo application during the trial, in order to meet a potential request from medical staff (or arc or tec) and/or patients. In the event of a bug fix, or non-substantial modification, the server may be put on hold. A system for updating the version on the “device” side can be used (telephone, pc).

The traceability of the software version used during the clinical investigation will be recorded on secure databases for the duration of the study and for a period of 10 years from the end of the study.

1. The populations and indications for which the experimental device is intended

COBOX is a medical software intended for the measurement of clinical parameters of heart rate and respiratory rate, in a medicalized or non-medicalized environment. COBOX is a solution intended to be used by healthcare personnel and lay users. As part of this test and in order to validate its performance, the COBOX device will be used by health professionals in real conditions of use.

As part of the study, the COBOX device is intended to be used:

- For measuring HR and RR in a clinical setting or at home for regular pathology monitoring or teleconsultation.
- In the context of reception and emergency care by trained personnel .
- On patients defined by the inclusion or exclusion criteria of this protocol.

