- Establish and verify the clinical safety of COBOX and detect any adverse side effects under normal conditions of use of the device and assess whether these constitute an acceptable risk in relation to the expected benefits of the device concerned.
- Evaluate ergonomics and user feedback.
- Evaluate the ease of use of the device (assessed by an ad-hoc questionnaire completed by the caregivers (or arc or tec), one questionnaire per caregiver and per type of device).

Justification of methodological choices

We are carrying out an observational, multicenter, prospective clinical investigation, evaluating the performance of the COBOX device in the context of and within the framework of usual care. Heart rate and respiratory rate are two physiological parameters measured when a patient arrives at the emergency room, so, given the high attendance of these services, it seemed to us to be an excellent place for this study. This measurement is carried out as part of the patient's care pathway using reference technical processes for taking measurements via a CE marked device and a reference method of manual counting. The inclusions of patients consulting in the emergency department make it possible to quickly obtain both a large number of inclusions, and on the other hand, a great variability of the constants noted due to the various pathological states. This approach allows great reproducibility in all clinical situations and thus makes it possible to validate performance in different contexts. In addition, a medico-economic study of the tool will be carried out.

Hypotheses

- H_0 :Routine care measurements in French care services, taken by the COBOX solution are different from measurements obtained through the application of reference technical processes and a manual counting reference method.
- H_1 :The current care measurements in French care services taken by the COBOX solution are consistent with the measurements obtained via the application of the reference technical processes and a reference method of manual counting.

Claims and expected performance of the investigational device that need to be verified.

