COBOX is a tool for measuring cardiac and respiratory rhythm in routine clinical practice for patients outside intensive care and outside continuous monitoring. We expect a correlation coefficient of more than 0.7 between the COBOX measurements and those obtained using the reference method. Regarding the secondary endpoints, we expect average standard deviations

between COBOX and the reference methods of 5 bpm for the heart rate and 3 bpm for the respiratory rate.

Expected benefits

These data will validate the COBOX tool in terms of measurement performance compared to the results obtained through the application of reference processes for taking measurements using CE marked devices, as well as those obtained using the reference method of counting manual. Applications for taking physiological constants without contact have a wide field of application in the field of routine care and save medical time, increase quality by limiting manual copying errors and the risk of contamination.

6. Research design

Research scheme

This is an observational study, responding to Article 62.1 of the European medical device regulations, prospective, comparative.

Primary endpoint

The main judgment criterion will be the intra-class correlation coefficient between the measurement by COBOX and the measurement obtained thanks to the application of the reference processes for taking measurements via a measurement by a CE marked tool (for HR).

In order to ensure the repeatability of the device, three successive comparative measurements (each spaced 5 seconds apart) on the same patient will be carried out.

Secondary endpoints

The additional secondary judgment criteria will be:

- For RF (ranked criterion): comparison with a manual measurement following a reference method of manual counting according to good training practices for healthcare personnel trained in taking measurements (ide, as, internal external).
- The reliability of the reproducibility of the measurement
- The time in seconds dedicated to taking the parameters with and without the COBOX tool (time for installing and removing the tool if applicable, time for completing the medical file if applicable, effective time for taking the HR constants and FR).
- Assessment of treatment costs:
 - Pick-up times / delays
 - Total treatment costs (direct medical and non-medical costs)

Inclusion criteria

- Adult patient (18 years and over)
AND
- Patient consulting in the emergency department of a participating center
AND

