
QUANTIQ provides users with one tablet per site per physician. Delivery of a functional tablet in the event of a malfunction within 5 working days. Bug fix within 3 days in case of software malfunction with continuous information for professionals.

8. Research process

Research timeline

- Start of inclusions: Mid-July 2022
- Duration of the inclusion period: 2 months
- Duration of participation of each patient: The time of their passage in the IOA box (less than 30 minutes)
- Total research duration: 3 months

Summary of patient follow-up

- Oral information by the IOA. If necessary, an investigating physician can complete the information at the patient's request.
- Informed consent with electronic signature.
- Collection of the patient's age, gender and Fitzpatrick phototype.
- Collection of patient identification number.
- The nursing staff (or arc or tec) installs the oximeter on the patient's finger.
- The nursing staff (or arc or tec) starts COBOX and begins to count the breaths in parallel.
- After 15s, a first measurement is made by COBOX. The pulse oximeter reference result is acquired in parallel, associated with the patient ID number and stored with the COBOX result at the same time on an electronic database.
- After 20s (5s after the previous measurement), a second measurement is made by COBOX. The pulse oximeter reference result is acquired in parallel, associated with the patient ID number and stored with the COBOX result at the same time on an electronic database.
- After 25s (5s after the previous measurement), a third measurement is made by COBOX. The pulse oximeter reference result is acquired in parallel, associated with the patient ID number and stored with the COBOX result at the same time on an electronic database.
- After 30s, the nursing staff (or arc or tec) enters the number of breaths counted since the start. This result is converted into a respiratory rate (RR) then associated with the patient number and stored in the database.

The data is blocked on the database until the end of the study. At the end of the study, they will be sent to the coordinating centre.

In order not to disrupt the general operation of the emergency department and patient care, the usual patient circuit is not modified. The COBOX tool is used by the reception staff in a contemporary way to their usual collection of input parameters.

Collection of consent

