10. STATISTICAL ASPECTS

Study size calculation

Considering the results of the performance verification tests of the medical device under study, we have established the study hypotheses in connection with the calculation of the size of the study set out below:

Minimum acceptable value of the ICC correlation coefficient (ρ_0)	0.6
Expected value of the ICC correlation coefficient (ρ_1)	0.7
The number of observations per subject k	3
Two-sided significance level (α)	0.05
Power (1 - β):	90%
Minimum size (n)	226
Size at 30% safety margin	323

A final study size of 323 patients is retained; taking into account a rate of unusable data of 30% in order to maintain the statistical power of the study in the event of exclusion of outliers.

Statistical methods used

The analysis will carry an initial descriptive part. The qualitative variables will be expressed in frequencies (with their 95% CI), and the quantitative variables expressed in means (with their standard deviation) if the distribution is normal. Otherwise, the quantitative variables will be expressed as the median (with their interquartile range).

Then, we will perform a comparative analysis, using chi 2 tests (or Fisher's exact) for the qualitative variables and student test (or Mann-Whitney test if applicable) for the quantitative variables. For performance estimation, we will determine the intra-class correlation coefficient with its confidence interval and we will perform a graphical analysis of Bland and Altman. In addition, we will calculate the mean square errors between the measurement with COBOX and the reference measurements, and they will be expressed as a percentage.

All our analyzes will be carried out at the 5% significance level.

An analysis of the repeated and compared measurements between COBOX and the CE marked device (used during the technical reference process for taking measurements) for the heart rate will make it possible to evaluate the reproducibility of the COBOX on repeated measurements in the *COBOX Protocol Valid*

same individual. A secondary statistical analysis will be done for the measurement times T+5s and T+10s.

We will use imputation methods or sensitivity analysis for the management of missing data.

11. Access rights to source data and documents

Access to data

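### The sample size allows for excluding outliers, but nothing limits exclusion to technical faults or makes an all-pairs ICC primary

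*Combined protocol and SAP*

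**What the plan says.** Section 10 (Study size calculation) derives a minimum of 226 patients for testing an ICC of 0.7 against a minimum of 0.6. It then retains 323, allowing for 30% unusable data "in order to maintain the statistical power of the study in the event of exclusion of outliers".

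The research summary (Section 1, Statistical analysis of data) says the two study samples will be compared by t and F tests, and then adds: "A DIXON test will be performed to assess the presence of statistically outliers within the samples". Section 10 does not mention this test.

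Section 6 makes the heart-rate ICC the primary endpoint, and Section 10 adds a Bland-Altman analysis and mean square errors. Neither defines the set of pairs analysed. Section 10 mentions imputation or sensitivity analysis, but for missing data only.

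On readings per patient, Section 6 says "three successive comparative measurements (each spaced 5 seconds apart) on the same patient will be carried out", and Section 10 says "A secondary statistical analysis will be done for the measurement times T+5s and T+10s".

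Three other provisions come near the subject:
- Section 3 keeps a replica tablet to "reproduce any possible deviation in a measurement and to investigate whether it comes from the tablet or the clinical trial conditions".
- Section 8 states: "The data is blocked on the database until the end of the study".
- Section 12 leaves data validation and freezing to existing procedures.

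None of them says which values may leave the analysis. Section 15 gives the statistical analysis to the sponsor.

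**The concern.** The trial asks how far COBOX departs from the oximeter. A COBOX reading that is far off is therefore part of the result. Removing a pair because it is extreme selects the data on the outcome.

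The direction depends on what is removed:
- If COBOX errors go, the ICC rises, and the limits of agreement and the mean square error shrink.
- If genuine extreme heart rates go, between-patient variance falls and the ICC can fall. That would also work against the reason given in Section 5 for recruiting in emergency departments: "a great variability of the constants noted due to the various pathological states".

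At stake are the accuracy figures that users will rely on and, in some scenarios, whether the lower confidence limit clears 0.6. Because the sponsor does the analysis, a rule fixed in advance matters more than usual.

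**Working it through.** **1. The plan's own size.** Inputs from Section 10: minimum ICC 0.6, expected ICC 0.7, k = 3, two-sided 5%, power 90%.

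n = 1 + 2k(z₀.₉₇₅ + z₀.₉₀)² / [(k − 1)(ln C)²], with C = (1 + 3 × 0.6/0.4)/(1 + 3 × 0.7/0.3) = 5.5/8 = 0.6875.

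This gives n = 225.5, so 226. Then 226/0.70 = 322.9, so 323. Both figures reproduce. By the same formula, power is 97.3% if all 323 are analysed and 90.1% if 226 remain. The number is not in dispute.

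**2. Simulation inputs.**
- From the plan: n = 323, and 5 bpm, the expected standard deviation "between COBOX and the reference methods of 5 bpm for the heart rate and 3 bpm for the respiratory rate" (Section 5).
- Assumed: heart rate mean 85 and SD 15 bpm; failed COBOX readings uniform on 30-200 bpm; failure rates of 2%, 5% and 10%; one pair per patient, which fits the treatment of the later readings as secondary.
- Second case, assumed: SD of differences 13 bpm.

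With all error in COBOX, the failure-free ICC is about 15²/(15² + SD²/2). SD 5 gives 225/237.5 = 0.947. SD 13 gives 225/309.5 = 0.73, near the plan's expected 0.7.

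**3. The test.** Two-sided Dixon r22 at 5%, repeated until nothing is flagged, and flagged pairs dropped. The upper ratio is (x₍ₙ₎ − x₍ₙ₋₂₎)/(x₍ₙ₎ − x₍₃₎), with its mirror image below. The simulated critical value at n = 323 is about 0.216. The ICC is two-way, absolute agreement, single measure.

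**4. Results, before to after exclusion (limits are ± bpm).**

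| SD of other differences | Failures | Dixon applied to | ICC | Limits | Narrowing |
|---|---|---|---|---|---|
| 5 | 2% | each device | 0.826 to 0.867 | 18.7 to 15.8 | about 16% |
| 5 | 2% | differences | 0.826 to 0.906 | 18.6 to 12.8 | about 30% |
| 5 | 5% | each device | 0.684 to 0.697 | 27.3 to 26.3 | 4% |
| 5 | 5% | differences | 0.686 to 0.729 | 27.2 to 24.5 | 10% |
| 5 | 10% | each device | 0.525 to 0.525 | unchanged | 0% |
| 5 | 10% | differences | 0.523 to 0.529 | 37.3 to 37.0 | 1% |
| 13 | 2% | each device | not tabulated | 30.1 to 28.9 | 4% |
| 13 | 2% | differences | not tabulated | 30.0 to 27.8 | 7% |

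The effect fades as failures become common because extreme values then mask one another: the gap to the third most extreme value is small relative to the range.

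**5. Effect on the test against 0.6.** The size calculation tests 0.6 at two-sided 5%, so the relevant event is the lower 95% limit moving from at or below 0.6 to above it. With SD 13 and 2% failures, this happens in about 18% (each device) to 32% (differences) of simulated trials. With SD 5 and 5% failures it happens in about 1-8%. Counting only point estimates that cross 0.6 would understate this.

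**6. Unit and direction.** With three readings per patient (323 × 3 = 969) and a 2% failure shared by all three, Dixon on patient mean differences gives 0.826 to 0.909, and Dixon on the 969 reading differences gives no change. With no failures, SD 15, and 0.5% of patients with a true heart rate of 150-190, Dixon on each device's values lowers the ICC from 0.695 to 0.675.

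**The case against.** The strongest reply is that exclusion is only contingent. The 30% is a safety margin, the Dixon test is described as detecting outliers and not as removing them, and both devices' readings are stored together automatically, so an all-pairs ICC can always be computed. All of this is true, and it limits the point to an unspecified rule. It does not say which result is primary once a value is flagged.

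A second reply is that the summary is not wholly silent on how Dixon is applied. Coming straight after a comparison of the two samples, the wording more naturally means each device's values than the paired differences. This stands, and the smaller per-device figures should lead.

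A third is that 5 bpm is the plan's expected overall SD. Adding 2% failures brings the overall SD to about 18.6/1.96 = 9.5 bpm, nearly double. This also stands, and is why the SD 13 case is shown.

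A fourth is that any prespecified exclusion rule, reported with counts, would close the gap. It would close the reporting gap, but a purely statistical rule would still remove device error from the estimate.

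A reader might infer that the sponsor intends to discard up to 30% of pairs, or the most discordant ones. The documents do not support this: 30% is a planning allowance, no passage describes such trimming, and in these simulations Dixon removes few patients (about 3 of 323 at 2% failures when run on differences). Nor does the sponsor's role as analyst show any intent, since the data are held until the study ends.

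**Conclusion.** The point holds as a gap in the exclusion rule. The plan provides for outlier exclusion, names only a purely statistical test, and neither requires a technical cause nor makes the all-pairs analysis primary. The step from Dixon flag to exclusion is inferred.

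The likely effect is small to moderate and rests on the assumed failure rate, failure distribution, heart-rate SD and form of the test. At 2% failures the limits of agreement narrow by about 16% (each device) or 30% (differences) with an SD of 5 bpm, and by about 4-7% with an SD of 13 bpm. At 10% failures almost nothing changes. The test against 0.6 is most exposed when the true ICC lies near the planning values. It would go too far to say that the reported accuracy will be overstated, or that the conclusion against 0.6 is safe. This is a cheap improvement, and the sample size is sound on this point.

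**What to change.** Before the data are released, state in the SAP that:
- the primary heart-rate ICC and Bland-Altman analysis use every available COBOX/oximeter pair at the primary time point or points;
- a pair may be excluded only for a pre-listed technical fault (for example, the oximeter off the finger), recorded without reference to the COBOX-oximeter difference;
- Dixon flags serve only for data checks and for a labelled sensitivity analysis beside the primary result, stating whether the test is run on each device's values or on differences, and by patient or by reading;
- the 30% is an allowance for technically unusable recordings;
- the number of exclusions and the reasons are reported.

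The cost is wording only, and the size stays at 323. The downside is that the reported ICC may be lower and the limits wider than after exclusion.

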Source: AT Ayance, HS Ramírez, JMR Pérez and CGT Palacios, "Low-cost microcontrolled based wireless heart rate and oxygen saturation monitor," 2018 International Conference on Electronics, Communications and Computers (CONIELECOMP), 2018, pp. 176-180, doi: 10.1109/CONIELECOMP.2018.8327195.

The rPPG on the other hand works on the same basic principle as the PPG in reflection except that the ambient light plays the role of the LED and the camera the role of the photodetector (see figure 2).

[figure not shown]

Figure 2. Light path in skin for a) contact PPG b) remote PPG

Source: Verkruyse, Wim PhD*; Bartula, Marek MSc†; Bresch, Erik PhD‡; Rocque, Mukul MSc†; Mestah, Mohammed BSc†; Kirenko, Ihor PhD† Calibration of Contactless Pulse Oximetry, Anesthesia & Analgesia: January 2017 - Volume 124 - Issue 1 - p 136-145 doi: 10.1213/ANE.0000000000001381

In its current version, the technologies embedded in this SaaS platform (COBOX) allow remote tracking, calculation and processing of several biological markers (cardio-respiratory rate). The idea is therefore to transform any camera into a medical device. From this camera. It is a SaaS platform type product that can be integrated and integrated into any other existing or future device. The data can be sent to the patient and the practitioner or managed in real time by trained and qualified nursing staff.

Finally, for its operation, the SaaS API requires a high-speed internet connection and an image capture device by optical camera.

The objectives of this solution are multiple:

- Standardization & reproducibility of the measurement :

Taking the constant "manually" by observation is today the reference method for measuring the respiratory rate. According to good training practices for medical or paramedical nursing staff, this method consists of counting the respiratory movements (inspiration and expiration) of the rib cage for 30 seconds extrapolated to 1 minute (by multiplying the value by two). This technology makes it possible to standardize the measurement of the respiratory rate by a reproducible and repeatable method with considerably reduced operator bias.

- Save time by automating vital signs measurements

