In current practice, measurements of respiratory rhythms and frequencies are taken visually by identifying the movements of the rib cage: The operator (nursing staff or arc or medical or paramedical tec) in current practice counts the complete respiratory movements (inspiration + exhale) for 30 seconds and multiply by 2 to extrapolate the result to 1 minute (Cycles per minute).

This medical decision-making can therefore vary according to these results, 2 to 3 cycles per minute varying around a "risk zone" (Above 20 cycles/minute or below 12/minute) can decide to whether or not to put on oxygen (these results are always interpreted with the oxygen saturation). Beyond the lack of robustness and reproducibility of this measurement in routine care, the purely human intervention makes its regular or continuous monitoring complex and time-consuming.

Finally, this data without a real monitoring standard is data that is almost unusable in epidemiological and/or clinical research.

Potential side effects

There are no direct or indirect adverse effects for the patient identified to date.

Residual risks associated with the experimental device, as identified in the risk analysis report

After implementation of risk reduction actions (in accordance with document REC-M2-016 Product risk analysis of the Technical File), all the residual risks assessed are deemed acceptable.

Risks associated with participating in the clinical investigation

No associated risk has been identified, the non-inclusion measures having been identified in this regard. The data collected for the evaluation will be observational and the information provided by COBOX will not be used in clinical decision-making.

Possible interactions with concomitant medical treatments

No interactions have been identified.

Measures that will be taken to control or mitigate the risks

The COBOX application poses no risk to the patient.

Justification of the risk/benefit ratio

As stated previously, the implementation of the risk management process led to the absence of unacceptable residual risks for the conduct of this study. Furthermore, the assessment of the benefit/risk is the subject of provisions documented within the PRO-M2-004 Risk Management procedure.

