The information is compiled by the IOA and if necessary completed by a doctor. This information must make it possible to answer all the patient's questions concerning the objective, the nature of the constraints, the foreseeable risks and the expected benefits of the research. It also specifies the patient's rights in the context of a clinical investigation and verifies the eligibility criteria. A copy of the information note and the electronic consent form are then given to the patient by the investigating physician.

The consent form is electronic and must be signed before data can be collected for research. After electronic acceptance of the consent, a copy of the consent form is sent to the patient with his identification number allowing him at any time to ask the Sponsor to delete his data. For his part, the Sponsor only has access to the patient's identification number but his email address is not stored.

The data will include:

- Taking FC and FR by the reference method
- HR and FR taken by the COBOX tool at the same time as those of the reference tool.
- The patient's age, sex and Fitzpatrick phototype.

The different copies of the information notice and the consent form are then distributed as follows:

- A copy of the information note and the signed consent is given/sent by email to the patient.
- The original copy is kept by the investigating physician (even if the patient moves during the duration of the research) in a safe place inaccessible to third parties.
- When accepting the patient's participation on the electronic form. This is automatically sent to the Sponsor.

Search stopping rules

The temporary stoppage of the research can be pronounced by technical problems concerning the evaluated tool. The research stops definitively when the necessary number of subjects is reached and all the data allow the analysis.

Constraints related to research and possible compensation of subjects/patients

Patients can simultaneously participate in another research. No compensation is provided for in this study. The patient will not be registered in the national file of people who lend themselves to biomedical research.

9. Management of adverse events and new facts

In accordance with article 2 of regulation 745/2017, the following terms mean:

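### No operator code is listed for the manual respiratory-rate count and no operator effect is planned, so any interval or test for mean RR bias or the limits of agreement may be too narrow

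*Combined protocol and SAP*

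**What the plan says.** **On the manual count.** Section 3 (objectives of the solution) presents COBOX as "a reproducible and repeatable method with considerably reduced operator bias", which implies that the manual count carries operator bias. Section 4 (clinical advantages) makes the same case: "Beyond the lack of robustness and reproducibility of this measurement in routine care". It adds that differences of 2 to 3 cycles per minute near a threshold can bear on a decision.

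**On data capture.** In Section 8 (Summary of patient follow-up), one member of the nursing staff, or a study technician or research associate, starts COBOX, counts breaths for 30 seconds and enters the total. The result is stored against the patient number. The data list in Section 8 (Collection of consent) gives heart rate and RR by both methods and the patient's "age, sex and Fitzpatrick phototype". It has no field for the person who counted. Centre is recorded, because Section 13 builds it into the patient code.

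**On analysis.** Section 10 states: "For performance estimation, we will determine the intra-class correlation coefficient with its confidence interval and we will perform a graphical analysis of Bland and Altman". It also plans a Student test (or Mann-Whitney) for quantitative variables, with all analyses at the 5% level. The Research Summary likewise compares the two samples by Student's t test. The plan does not name an ICC model, an operator or centre term, or a clustered variance.

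**The concern.** If a counter tends to read high or low, every patient that person counts carries the same error in the RR difference. Those patients are then not independent pieces of information about RR bias. The standard formulas for the mean difference and the limits of agreement divide by the number of patients as if they were, so the intervals come out too short.

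The between-counter part of the disagreement also stays mixed into the total and is charged to COBOX. Removing that component is one of the sponsor's stated reasons for the device. Without an operator code it cannot be estimated afterwards. RR agreement is the first ranked secondary objective, so the result will be read closely.

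**Working it through.** **The plan's own figure.** Section 10 gives "Minimum acceptable value of the ICC correlation coefficient" 0.6, "Expected value of the ICC correlation coefficient" 0.7, "The number of observations per subject k" 3, "Two-sided significance level" 0.05 and power 90%. With the Walter-Eliasziw-Donner formula:

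- C0 = (1 + 3×0.6/0.4) / (1 + 3×0.7/0.3) = 5.5/8 = 0.6875
- n = 1 + 2(1.960 + 1.282)² × 3 / [(ln 0.6875)² × 2] = 225.53, so 226
- 226/0.7 = 322.86, so 323

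Both stated sizes reproduce. The k of 3 matches the three heart-rate readings. RR has one manual count per patient, so this is not an RR calculation.

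**Inputs for RR.** N = 323 (Section 10). SD of the COBOX-minus-manual difference = 3 cycles/min (Section 5, expected performance, read as the SD of a single paired difference). The number of operators J and the operator share ρ of the variance of that difference are not in the documents, so both are varied. With SD 3, shares of 5%, 10% and 20% correspond to operator-bias SDs of √(0.05×9) = 0.67, √(0.10×9) = 0.95 and √(0.20×9) = 1.34 cycles/min.

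**Formula.** With m = N/J patients per operator, the variance of the mean difference is multiplied by the design effect DE = 1 + (m − 1)ρ. An interval that ignores operator has coverage of about 2Φ(1.96/√DE) − 1.

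Example, J = 20 and ρ = 0.10: m = 16.15, DE = 1 + 15.15×0.10 = 2.51, √DE = 1.59, coverage about 78%. The naive half-width 1.96×3/√323 = 0.33 would need to be about 0.33×1.59 = 0.52.

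**Results for mean RR bias** (coverage from simulation, 4,000 runs per cell, equal patients per operator):

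| Operators | DE at ρ = 5 / 10 / 20% | Coverage of nominal 95% interval |
|---|---|---|
| 8 | 2.97 / 4.94 / 8.88 | 75 / 62 / 49% |
| 20 | 1.76 / 2.51 / 4.03 | 86 / 78 / 65% |
| 40 | 1.35 / 1.71 / 2.42 | 91 / 86 / 79% |
| 80 | 1.15 / 1.30 / 1.61 | 93 / 91 / 88% |

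At a 1% share, DE runs only from 1.39 (8 operators) down to 1.03 (80). If the Student test is run paired, its false-positive rate is 100% minus the coverage: for 20 operators, about 14 to 35% instead of 5%.

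**Limits of agreement.** With 226 patients, nominal 95% intervals for the upper limit covered 85% and 70% (12 operators, operator SD 1.0 and 1.5), and 89% and 79% (20 operators, same SDs).

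**ICC** (one-way, F-based 95% interval, true ICC 0.7, N = 323). Coverage at shares of 5 / 10 / 20%:

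- 8 operators: 94.6 / 93.1 / 89.0%
- 20 operators: 94.9 / 94.4 / 92.4%
- 40 operators: 94.8 / 95.0 / 94.0%

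**The case against.** The strongest reply is that the plan names a confidence interval only for the ICC, and that interval barely moves. Bland-Altman is described as graphical, with no interval for the bias or the limits, and no success criterion rests on mean RR bias. This stands, and it limits the point to any bias or limits interval that is reported and to the Student comparison. That comparison is affected as shown only if it is paired, which the plan does not say.

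A reader might infer that a few operators will count everyone, that the plan assumes independent patients, and that the RR intervals are therefore too narrow as a matter of fact. The documents do not support that. They give neither the number of operators nor their variability, and they are silent on independence. With many counters or small operator bias the effect nearly vanishes.

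The data list in the consent section is also not exhaustive: it omits the timing, cost and questionnaire data planned elsewhere. Section 3 stores tablet references and allows application use to be monitored. These are at best weak proxies for who counted. An operator field may exist, but none is described.

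A reader might also infer that an operator effect would isolate COBOX error. It would not. With one count per patient, within-operator counting error stays in the residual. The same person starts COBOX, so the operator effect may include set-up and site conditions.

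**Conclusion.** The point holds in conditional form. The protocol itself calls the reference operator-dependent, lists no operator identifier and plans no operator or centre effect for RR. Intervals or tests for mean RR bias and intervals for the limits of agreement may therefore overstate precision, and between-operator variance could not be recovered later.

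The loss could be large (coverage near 50% with 8 operators and a 20% share) or slight (93% with 80 operators and a 5% share). It rests on assumed operator numbers and shares, equal workloads and the expected SD of 3. It also eases with fewer analysed patients: at N = 226, 20 operators and a 10% share, DE is 1 + (11.3 − 1)×0.10 = 2.03 and coverage about 83%, against 78% at N = 323.

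The ICC interval is little affected. The primary heart-rate comparison uses the oximeter and is not affected. This is a cheap improvement to a secondary endpoint and does not threaten the trial's main conclusion.

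**What to change.** 1. Add one mandatory, pseudonymised operator code to the tablet session record for whoever counts the breaths. Centre is already in the patient code.
2. State the ICC model for RR, and whether the Student comparison is paired.
3. Report RR bias and limits of agreement, with intervals, from a model of the differences with operator (within centre) as a random effect, or from a bootstrap that resamples operators. Apply the same adjustment to any 5% test of mean RR bias.
4. Report the between-operator variance, the number of operators and the patients per operator. Do not label the residual as COBOX error, because it still contains within-operator counting error.
5. If operator was not captured, give a centre-level sensitivity analysis and say that four centres are too few for it to be firm.

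**Cost:** one tablet field, a model change and wider RR intervals. In simulations with 226 patients, 12 to 20 operators and operator SD 1.0 to 1.5, operator-clustered intervals for mean bias covered 93.5 to 96.5%. Their mean widths were 1.23 to 2.04 cycles/min against 0.78 for the naive interval, or 1.6 to 2.6 times as wide.
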